3.6 Explanation for choice of comparator (or placebo)

(SPIRIT #6b)

The Pfizer / BioNTech COVID-19 vaccine, BNT162b2 (30 µg) Comirnaty®, is administered intramuscularly (IM) as a series of two 30 µg doses of the diluted vaccine solution (0.3 mL each) according to the following schedule: a single dose followed by a second dose, waiting at least 21 days later (recommended: 28 days in Switzerland) and the vaccine was licensed by Swissmedic December 19, 2021 (12).

3.7 Risks / Benefits

(ClinO, Appendix 4, 3.5; Art 25d2; ICH/E6 6.2.3; SPIRIT #6a; MD: ISO 14155 Annex A & ISO 14971)

ICH: Summary of the known and potential risks and benefits, if any, to human subjects.

In December 2020 between 80 to 100 individuals in Switzerland died per day from Covid-19. Actual rates are lower following more stringent public health measures with a partial lock-down, but rising mutant infections with higher transmission rates are of concern. Introduction of vaccines is the only valid strategy to confine the pandemic by inducing a sufficiently high herd immunity. At the forefront of

the vaccine strategy by BAG is the vaccination of the elderly and frail population suffering from comorbidity. The current trials addressed the very important issue of vaccine induced immunogenicity and safety data in immune-compromised individuals who were not or only to a very limited extend included into the ongoing phase III vaccine trials by Pfizer / BioNTech and Moderna.

The so far existing evidence for both vaccines to be compared in the current trial show strong immune responses in the short observation periods of roughly 60 days, suggesting that both vaccines confer protection against Covid-19 and complications from Covid-19 infection (10, 11).

The potential risk conferred by the vaccines as judged by the safety profile which indicate mostly mild adverse events and a very low incidence of severe adverse events with no apparent marked differences between the vaccine and placebo groups.

Vaccine efficacy for both vaccines was well above 90% in the pre-planned interim analysis (6, 7).

However, it is not known to what extend the actually available immunogenicity, vaccine efficacy and safety data relate to immune compromised individuals. In both phase III trials of vaccines by Pfizer / BioNTech and Moderna no patients with organ transplants were included. In the trial by Pfizer / BioNTech and Moderna there were 121 and 179 HIV positive individuals included (6, 7). No subgroup data on trial efficacy and safety of these individuals and on the level of immunosuppression in this sub-population was reported. Also no data on immune response in HIV positive patients was reported. The present trial fills in this evidence gap by comparing the first two licensed vaccines in Switzerland against Sars-CoV-2 in immune compromised hosts. Nesting the trial into an existing cohort infrastructure allows for the monitoring of vaccine efficacy and long-term safety in an efficient and cost-saving way

3.8 Justification of choice of study population

According to the recommendation by the Bundesamt für Gesundheit (13) the following conditions define patient groups of high priority of vaccinations which include the primary target groups of this trial i.e. patients with HIV infection, solid organ transplantation and patients with these basic conditions plus additional comorbidities. The guidelines stress that due to the limited evidence on safety and efficacy of vaccines against SARS-CoV-2 patients with acquired immune deficiency and immune-suppressive therapy decision for vaccination has to be taken by the treating clinicians by considering risks and benefits for the individual patient.

Comorbidity / Category organ system	Priority Grouping 1: High risk BGP (Detailed definitions)
Heart diseases	
 -congestive heart failure NYHA II -Symptomatic chron. Ischemic coronary heart disease
Hypertension	
 - Hypertension with systolic blood pressure > 160 mm HG regardless of antihypertensive therapy - Hypertension with cardiac complications and end organ damage
Pulmonary diseases	
 - COPD, stage GOLD II or above - Emphysema/severe bronchiectasis - Pneumopathy / Lung fibrosis - lung disease with severe reduction of vital capacity
Kidney diseases	
 - Severe chronic kidney disease with GFR <30ml/min/174m²
Diabetes	
 - Diabetes (Type 1 or 2) with relevant organ damage or HbA1c ≥8%

Obesity

- BMI ≥ 35 kg/m².

Immunodeficiency*, inborne and acquired diseases and im- muno-suppressive therapy

Relevant immunodeficiency with

- malignant haematological disease
- Neoplasia/cancer under active therapy
- immune-mediated inflammatory diseases (e.g.. systemic lupus erythematoses, rheumatoid arthritis, psoriatic disease, chronic inflammatory bowel disease), with immunosuppressive therapy (including prednisolone-equivalent >20 mg/day, steroid-sparing therapy and biologicals).
- HIV-Infection with CD4+ T cells < 200 / μ L.
- Organ transplantation, bone marrow or stem-cell transplantation, individuals on waiting list for transplantation

4. STUDY OBJECTIVES

4.1 Overall Objective

We refer to the master protocol.

4.2 Objectives related to platform trial set-up and feasibility of cohort based patient recruit, trial inclusion and data collection

We refer to the master protocol.

4.3 Objectives related to a platform based nested pilot trial to investigate the comparative effectiveness of vaccines against Sars-CoV-2

The study seeks to determine the following SARS-CoV-2 related objectives (for detailed definitions see under 5 study endpoints) which are all developed according to FDA recommendations for phase III Covid-19 vaccine licensing trials (14):

- Immune response (pan-Ig antibodies against the receptor-binding domain (RBD) in the S1 subunit of the spike protein (pan-Ig anti-S1-RBD) of SARS-CoV-2.
- Newly PCR-confirmed asymptomatic SARS-CoV-2 infection,
- Newly PCR-confirmed symptomatic SARS-CoV-2 infection
- Severe COVID-19 infection,
- COVID-19 burden of diseases (BOD)
- Patient reported asymptomatic or symptomatic infections of household members.
- Safety parameters
 - Adverse events from vaccines and
 - Serious adverse events

4.4 Safety Objectives

To evaluate the safety of vaccines in immunocompromised patients and risks for adverse events (AEs) and serious adverse events (SAEs).

5. STUDY OUTCOMES

For the feasibility outcomes we refer to the master protocol.

5.1 Immunological Outcomes

The primary immunological endpoint are antibodies to the SARS-CoV-2 spike (S1) protein receptor binding domain (RBD) in human serum and plasma assessed by the commercial immunoassay

Elecsys® Anti-SARS-CoV-2 S for the in vitro quantitative determination (15). This assay detects pan-Ig antibody response (pan-Ig anti-S1-RBD) and allows for a quantitative assessment of the serological response of the participants at baseline and three months after vaccination. Additionally, we will qualitatively measure anti-Nucleocapsid (N) responses with Elecsys® Anti-SARS-CoV-2 N assay to gain a broader insight on the immune response of the participants.

In addition SARS-CoV-2-binding antibody responses of the participants by analyzing the IgM, IgA and IgG responses to a wider range of SARS-CoV-2 proteins (S1, S2, RBD and N using an in-house method (ABCORA 2.0) established at the Institute of Medical Virology (IMV), UZH) will be measured. The ABCORA 2.0 test has an advantage over commercial available tests, as it allows a parallel assessment of IgG, IgM and IgA reactivity to multiple antigens enabling a high-dimensional temporal resolution of antibody responses and a dissection between humoral responses to an infection and vaccination

5.2 Clinical Outcomes

The clinical effectiveness endpoints are (according to FDA recommendations for phase III Covid-19 vaccine licensing trials (14)) the following:

- Newly PCR-confirmed asymptomatic COVID-19 infection (identified by the presence of anti-SARS-CoV-2 nucleocapsid antibodies or SARS-Cov-2 PCR or rapid antigen test) and no related symptoms [(i.e. fever or chills, cough, shortness of breath or difficulty breathing, fatigue, muscle or body aches, headache, new loss of taste or smell, sore throat, congestion or runny nose, nausea or vomiting, and diarrhea)] at any time point in within 48 weeks following randomisation.
- Newly PCR-confirmed symptomatic COVID-19 infection with at least one of the following symptoms (i.e. fever or chills, cough, shortness of breath or difficulty breathing, fatigue, muscle or body aches, headache, new loss of taste or smell, sore throat, congestion or runny nose, nausea or vomiting, and diarrhea at any time point in within 48 weeks following randomisation
- severe COVID-19 infection with respiratory failure, evidence of shock (as diagnosed by a treating physician), clinically significant acute renal, hepatic, or neurologic dysfunction; admission to an intensive care unit; and death at any time point in within 48 weeks following randomisation.
- COVID-19 burden of diseases (BOD), a composite of the above endpoints. The BOD is will be scored as by using 0 for no COVID-19, 1 for non-severe COVID-19, and 2 for severe COVID-19.

An additional clinical effectiveness endpoint is patient reported asymptomatic or symptomatic infections of household members.

All clinical outcomes will be measured in the trial database during a follow-up period of 48 weeks after randomisation and vaccination.

5.3 Other Outcomes of Interest

None.

5.4 Safety Outcomes

5.4.1 Collection of solicited local and systemic adverse events will for feasibility reasons be reduced to:

- any local symptom (redness or swelling or prolonged pain at injection side) limiting continuation of normal daily activities during the first 7 days after vaccination
- any systemic symptom (fever, generalized muscle or joint pain) limiting continuation of normal daily activities during the first 7 days after vaccination
- any vaccine related symptom leading to contacting a physician during the first 7 days after vaccination

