10.1.3 Assessment of safety outcomes

10.1.3.1 Vaccine specific adverse events

Patients will be asked at the 4 week study visit about the following specific vaccine related adverse events:

- Any symptoms at injection site (redness, swelling or pain) limiting continuation of normal daily activities during the first 7 days following the booster vaccination?
- Any systemic symptoms (fever, muscle pain, joint pain) limiting continuation of normal daily activities during the first 7 days following the booster vaccination?
- Any vaccine related symptoms leading to physician contact during the first 7 days following the booster vaccination?

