Safety data from a November 11, 2020 interim analysis of approximately 30,350 participants ≥18 years of age randomised 1:1 to vaccine or placebo with a median of 7 weeks of follow-up after the second dose supported a favorable safety profile, with no specific safety concerns identified that would preclude issuance of an EUA. These safety data are the primary basis of FDA's safety review. On December 7, 2020, the Sponsor submitted additional follow-up data from these participants with a cut-off of November 25, 2020, which represents a median of 9 weeks (>2 months) of follow-up post-dose 2. Key safety data from this later submission, including death, other serious adverse events, and unsolicited adverse events of interest were independently verified and confirmed not to change the safety conclusions from the interim safety analysis.

The most common solicited adverse reactions associated with mRNA-1273 were injection site pain (91.6%), fatigue (68.5%), headache (63.0%), muscle pain (59.6%), joint pain (44.8%), and 6 Moderna COVID-19 Vaccine VRBPAC Briefing Document chills (43.4%); severe adverse reactions occurred in 0.2% to 9.7% of participants, were more frequent after dose 2 than after dose 1, and were generally less frequent in participants ≥65 years of age as compared to younger participants. Among unsolicited

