9.2.4 Assessment of safety outcomes

9.2.4.1 Adverse events following vaccination

Any local symptom (redness or swelling or prolonged pain at injection side) continuation of normal daily activities during the first 7 days after vaccination

During the 12-week visit, patients will be asked if they had any local symptoms which limited their daily activities during the first 7 days after vaccination.

- Any systemic symptom (fever, generalized muscle or joint pain) limiting continuation of normal daily activities during the first 7 days after vaccination.

During the 12-week visit, patients will be asked if they had any systemic symptoms after randomisation which limited their daily activities during the first 7 days after vaccination.

- Any vaccine related symptom leading to contacting a physician during the first 7 days after vaccination

During the 12-week visit, patients will be asked if they had to contact a physician within 7 days after vaccination.

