11.4.5 Safety analysis

Results from a phase 3 randomised, observer-blinded, placebo-controlled trial conducted at 99 centers across US on 30,420 volunteers reported that no safety concerns were identified, aside from transient local and systemic reactions for the COVID-19 mRNA Vaccine Moderna®. For BNT16b2 vaccine Comirnaty® (Pfizer / BioNTech), a randomised placebo-controlled trial on 43,548 participants showed short-term, mild-to-moderate pain at the injection site, fatigue and headache. The incidence of serious adverse events was low and similar in the vaccine and placebo groups (6). Therefore, we expect safety issue to be small and do not believe that we will have enough power to demonstrate any statistical difference between the treatment arms.

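### The solicited systemic-reaction item lists only fever, muscle pain and joint pain, leaving out fatigue, headache and chills; this matters most in the third sub-protocol, where the list is part of the patient question

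*Combined protocol and SAP*

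**What the plan says.** Section 5.4 of the first sub-protocol states that "Collection of solicited local and systemic adverse events will for feasibility reasons be reduced to" three items: a local one, a systemic one and one that depends on contact with a doctor. The systemic item is "any systemic symptom (fever, generalized muscle or joint pain) limiting continuation of normal daily activities during the first 7 days after vaccination". The third item is "any vaccine related symptom leading to contacting a physician during the first 7 days after vaccination".

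Section 9.2.4.1 of the same document repeats the systemic item with the same bracket. It then says how, at the 12-week visit, the information is obtained: "patients will be asked if they had any systemic symptoms after randomisation which limited their daily activities during the first 7 days after vaccination". That sentence contains no symptom list.

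Section 10.1.3.1 of the third sub-protocol puts the item as a question at the 4-week visit, with the list inside it: "Any systemic symptoms (fever, muscle pain, joint pain) limiting continuation of normal daily activities".

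Two places in the first sub-protocol describe what these vaccines cause. Section 3.4 gives, for mRNA-1273, "injection site pain (91.6%), fatigue (68.5%), headache (63.0%), muscle pain (59.6%), joint pain (44.8", followed by chills at 43.4%. Section 11.4.5 says that the large placebo-controlled trial of Comirnaty "showed short-term, mild-to-moderate pain at the injection site, fatigue and headache".

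**The concern.** A prompted question records mainly what it prompts for. Here the prompts leave out the two systemic reactions that the plan's own evidence puts first for one vaccine and names for the other. A patient who stayed at home for two days with fatigue and headache, without fever or muscle or joint pain, could properly answer no to the third sub-protocol's question. The contact item would record that patient only if a doctor was contacted.

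The recall interval makes the prompts matter more. The question about the first 7 days is put at 4 weeks in the third sub-protocol and at 12 weeks in the first.

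At stake is the descriptive rate of activity-limiting systemic reactions. Both documents say that evidence in immunocompromised patients is lacking (first sub-protocol, section 3.1; third sub-protocol, section 5.2), so this rate is among the results that readers will want.

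**Working it through.** The plan has no calculated figure to reproduce here. The check compares the symptom list with the reaction frequencies and asks what those frequencies can say about size.

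**Step 1. List against evidence** (frequencies from section 3.4 of the first sub-protocol: mRNA-1273, any severity).

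| Systemic reaction | Frequency | In the item? |
|---|---|---|
| Fatigue | 68.5% | no |
| Headache | 63.0% | no |
| Muscle pain | 59.6% | yes |
| Joint pain | 44.8% | yes |
| Chills | 43.4% | no |

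Fever is in the item but has no frequency in that list. Of the five reactions with a frequency, two are asked about and three are not. The two omitted at the top exceed the commonest listed symptom by 68.5 − 59.6 = 8.9 and 63.0 − 59.6 = 3.4 percentage points. For Comirnaty, section 11.4.5 gives names without frequencies; both systemic reactions it names, fatigue and headache, are absent from the item.

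**Step 2. Is the list exhaustive?**

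- First sub-protocol, section 5.4: collection is reduced to the items shown, and the bracket has no marker such as e.g. This suggests a closed list.
- First sub-protocol, section 9.2.4.1: the bullet keeps the bracket, but the sentence on what patients are asked is open. This suggests an illustrative list.
- Third sub-protocol, section 10.1.3.1: the items are introduced as specific events to be asked about, and the bracket is inside the question. This suggests a closed list.

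The case report form would settle the matter for the first sub-protocol, but it is not in the documents.

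**Step 3. Can the possible miss be sized?** The relevant share is patients with fatigue or headache but no listed symptom. Only the separate frequencies are given, so only bounds follow. For fatigue without muscle or joint pain:

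- Upper bound: min(68.5, 100 − max(59.6, 44.8)) = 40.4%.
- Lower bound: max(0, 68.5 − min(100, 59.6 + 44.8)) = max(0, 68.5 − 100) = 0%.

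Headache gives the same bounds: min(63.0, 40.4) = 40.4%, and max(0, 63.0 − 100) = 0%. If one assumes that joint pain occurred only with muscle pain, the lower bounds become 8.9% for fatigue and 3.4% for headache. Fever, for which no frequency is given, could lower these again.

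A range of 0% to 40.4% is too wide to be useful, and it is for reactions of any severity. The endpoint counts only reactions that limit activity. Section 3.4 puts severe reactions at 0.2% to 9.7% without a breakdown by symptom, so the ranking at the endpoint's threshold is unknown.

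**Step 4. Carry-over to the third sub-protocol.** The frequencies come from the trial of the two-dose monovalent vaccine. The third sub-protocol gives no symptom frequencies for the bivalent vaccines. Its section 5.2 cites similar reactogenicity for the mRNA-1273.214 and mRNA-1273 boosters. Applying the ranking to the bivalent booster is therefore an assumption, though a reasonable one.

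**The case against.** The strongest reply is that the first sub-protocol asks an open question. On the wording of its section 9.2.4.1, a patient kept in bed by fatigue answers yes and nothing is lost. This stands for that document, as far as showing that a closed list was not necessarily used. It does not remove the inconsistency with section 5.4, and it does not help the third sub-protocol, whose question contains the list.

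A second reply is that the reduction is disclosed and made for feasibility. That explains having three questions rather than a diary. It does not explain why, within one yes/no question, commoner symptoms gave way to less common ones. Both documents also use a longer list that includes chills, fatigue and headache when defining symptomatic COVID-19 (first sub-protocol, section 5.2; third sub-protocol, section 10.1.2), so length was not a barrier elsewhere.

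A third reply is that safety is descriptive. Section 11.4.5 of the first sub-protocol expects too little power to show a difference, and serious adverse events and doctor contacts are collected separately. This stands, and it limits the importance of the point. It does not answer the concern about coverage, because a question that misses events gives a low rate at any sample size.

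A reader might infer that the item treats the vaccines unequally, since it names pains reported for mRNA-1273 and neither systemic reaction named for Comirnaty. The documents do not support this. The Comirnaty text is a one-sentence summary, and its silence on muscle and joint pain is not evidence that they are absent. Fatigue and headache also lead the mRNA-1273 list, so the omission touches both vaccines.

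**Conclusion.** The item omits fatigue, headache and chills, and the omission is clearest in section 10.1.3.1 of the third sub-protocol. In the first sub-protocol the documents leave open whether the list was exhaustive. Activity-limiting systemic reactions managed at home may be under-counted.

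A reader might go further and put a figure on the loss, or say that these are the commonest activity-limiting reactions to both vaccines. Neither is supported: frequencies exist only for mRNA-1273 and only at any severity, and the bounds from them start at zero. No direction of bias between vaccines can be inferred.

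For the third sub-protocol, the conclusion assumes that the question is put as written and that the reaction profile of the monovalent vaccine broadly applies to the bivalent booster. The point is minor: a cheap improvement to a descriptive safety item, with no effect on the primary immunological endpoint or the sample size.

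**What to change.** In section 10.1.3.1 of the third sub-protocol, change the bracket to (e.g. fever, chills, fatigue, headache, muscle pain, joint pain) and use the same words on the case report form.

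In the first sub-protocol, align sections 5.4 and 9.2.4.1 with the open question that 9.2.4.1 describes. The third sub-protocol reports that sub-study as already conducted, so the data cannot change. The practical step is to state in its report exactly which wording patients were given.

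The cost is three added symptoms and an e.g. on an existing question, with no extra visit or item. The recorded rate may be somewhat higher, and results will be less comparable word for word with data collected under the three-symptom list. A sentence in the report can disclose this.

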6. STUDY DESIGN

6.1 General study design and justification of design

This is a pilot trial which is based on a trial platform that is integrated into the ongoing routine prospective data collection of two national cohorts, the SHCS and STCS. Eligibility of trial participants will be checked from routinely collected cohort data. Baseline data collection is done within cohorts. Randomisation and follow-up data collection of clinical trial endpoint data is done within the trial platform which is linked to the cohort database. The trial platform is overseen and managed by the two data centres of the SHCS and STCS.

A parallel two-arm, open-label randomised controlled pilot trial comparing the first approved SARS-CoV-2 vaccines (Comirnaty® by Pfizer/ BioNTech and COVID-19 mRNA Vaccine Moderna® by Moderna) is planned to compare the immunogenicity, clinical effectiveness and safety of the first two licensed vaccines against Sars-CoV-2.

Enrolment of patients is explained in figure 1 of the master protocol. Cohort data centres will identify eligible patients based on routinely collected cohort data and eligible patients will be flagged according to the priority vaccination criteria by the BAG and contacted for consent for participation prior to randomisation. Randomisation will be performed through minimisation with respect, center, age (<65, ≥65 years old), sex, immune-suppression (<200 CD4 cells/μl in SHCS and uninterrupted prednisone treatment of at least 6 months in addition to standard immunosuppression in STCS) and a random element that reduces randomisation predictability. The minimisation will be conducted for each cohort separately. The trial platform allows to expand the pilot trial and to add further sub-study protocols to evaluate for example vaccine strategies in patients with a first vaccination but insufficient or lacking immune response (Figure 1 master protocol)

